occlusion, vascular reconstruction surgery can still successfully restore blood flow and achieve good therapeutic effects. However, currently, the vascular reconstruction treatment for chronic MCA occlusion is mainly limited to case reports, and there is a lack of systematic prospective studies to verify the safety and effectiveness of these treatments.

Given the above background, this study aims to fill this research gap by systematically evaluating the efficacy and safety of stent placement in patients with chronic MCA occlusion through prospective clinical trials, in order to provide more scientific and standardized treatment guidance for such patients.

II. Research Purpose

The aim of this study is to evaluate the safety and effectiveness of stent placement in patients with chronic MCA occlusion, and to explore its impact on blood flow recovery, reduction of reocclusion rate, and improvement of neurological function recovery.

III. Research Methodology

1. Research Design

This study adopts a prospective, single center, observational clinical trial design. By setting up a stent group and a control group, the therapeutic effects of the two groups of patients were compared to evaluate the safety and effectiveness of stent placement in patients with chronic middle cerebral artery (MCA) occlusion. This study has been approved by the Clinical Ethics Committee of Huishou Central People's Hospital in terms of human research ethics, and strictly adheres to relevant ethical standards and guiding principles.

2. Study Participants

Selection Criteria:

- 1) Age 18 and above, male and female unlimited.
- 2) Chronic occlusion of MCAconfirmed by magnetic resonance imaging (MRI) or computed tomography (CT), lasting more than 3 months.
- Neurological deficits caused by MCA occlusion, such as hemiplegia, speech disorders, etc.
- 4) Have not received MCA stent revascularization treatment in the past three months.

Exclusion Criteria:

- 1) Acute stroke occurred within the past three months.
- Severe heart disease, liver and kidney dysfunction, cerebral hemorrhage, active bleeding, or coagulation dysfunction.
- 3) Allergy to contrast agents.
- 4) Serious mental illness or inability to comply with research requirements.
- 5) Pregnant or lactating women.
- 6) MCA occlusion was found without any symptoms.
- 7) Participated in other clinical trials within the past six months.

3. Research Process

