Participants first undergo detailed screening to ensure that they meet the inclusion and exclusion

criteria. Afterwards, all patients or their legal representatives are required to sign an informed consent form. Subsequently, patients will be randomly assigned to either the stent group or the control group. The control group received aspirin treatment, while the stent group underwent stent placement surgery on the basis of aspirin treatment.

4. Stenting Method

The patient underwent whole brain angiography in the intervention room, and the Seldinger technique was successfully used to puncture the right femoral artery and insert a 5F sheath. Insert the 5F pigtail catheter and vertebral artery catheter sequentially through the sheath tube for angiography to identify occlusion of left or right MCA. Next, the MCA stent is inserted, and the 0.014-inch microwire and microcatheter are successfully navigated to the left or right MCA occlusion site through the catheter. Then, the microcatheter is exchanged, and an appropriately sized intracranial self expanding stent is placed and released. After surgery, the femoral artery puncture site was sutured using a vascular closure device.

IV. Statistical Analysis

Use R software (version 4.1.2) for statistical processing. Classified data is presented in frequency and percentage, while continuous data is represented in mean \pm standard deviation or median and interquartile range. Inter group comparisons were conducted using methods such as independent sample t-test, Mann Whitney U test, chi square test, or Fisher's exact test.

V. Research Plan

Preparation phase (March 2021- April 2021): Obtain ethical approval, prepare and review all research documents (including informed consent forms and research protocols), and

establish a data management system.

Recruitment stage (May2021 November 2021): Identify eligible patients through the neurology and interventional radiology departments of collaborating hospitals, screen for inclusion and exclusion criteria, and obtain informed consent from patients.

Treatment stage (December 2021- January 2022): Arrange stent placement surgery or start standard drug treatment for eligible patients.

Follow up stage (February 2022- February 2023): Regular follow-up will beconducted on all participants to evaluate treatment outcomes, including blood flow recovery, reocclusion rate, and neurological function recovery. The follow-up time points is 3 months after surgery.

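### Safety is a stated aim, but the plan names no safety outcome, and its single time point, 3 months after surgery, misses early procedural harm and is undefined for controls

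*Combined protocol and SAP*

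**What the plan says.** Section II opens with: "The aim of this study is to evaluate the safety and effectiveness of stent placement in patients with chronic MCA occlusion". Section III.1 repeats safety as a reason for comparing the two groups.

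Section III.3 describes random assignment and the two regimens: "The control group received aspirin treatment, while the stent group underwent stent placement surgery on the basis of aspirin treatment". Section III.4 describes the procedure and ends with closure of the puncture site.

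Section V sets the timing. The treatment entry reads "Treatment stage (December 2021- January 2022): Arrange stent placement surgery or start standard drug treatment for eligible patients". The next entry, "Follow up stage (February 2022- February 2023", says: "Regular follow-up will beconducted on all participants to evaluate treatment outcomes, including blood flow recovery, reocclusion rate, and neurological function recovery". It then gives the one time point: "The follow-up time points is 3 months after surgery". Data collection and comparison of the groups are described for March to September 2023.

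Section IV lists general two-group tests, Fisher's exact test among them. It mentions no safety analysis and no look at the data during treatment.

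**The concern.** Stroke, intracranial haemorrhage and death are the harms one would most want counted after an intracranial stent procedure, and the added risk in the stent group starts with the procedure. The plan does not name any of them as an outcome. Haemorrhage and bleeding appear only as exclusion criteria, and acute stroke only as an exclusion for the preceding three months.

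Three things are at stake. First, a disabling procedural stroke might enter the data only as poor neurological recovery at 3 months, and the plan does not say how a death before then is handled. Second, with no named safety outcome and no time origin for controls, the comparison that Section II promises is not specified. Third, if several early patients are harmed, nothing written requires anyone to look at the running count before the next stent is placed. Section I says that evidence for this treatment consists mainly of case reports, so there is little outside experience to rely on instead.

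**Working it through.** The plan states no sample size, event rate or safety threshold, so there is no figure of its own to reproduce. The check is a reading of the text followed by calendar arithmetic.

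**1. Is a safety outcome named?** Section II states the aim without an outcome. Section III.2 mentions haemorrhage, bleeding and stroke only as eligibility criteria. Section III.4 says nothing about recording complications. Section IV has no safety variable. Section V names three outcomes, none of which is stroke, haemorrhage or death. Reocclusion could be seen as a device failure, but it is not labelled a safety outcome and would not register a haemorrhage or a death.

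**2. When is the first scheduled assessment, relative to the last stent?** Section V gives months only, so I take the widest treatment window, 1 December 2021 to 31 January 2022.

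- Earliest 3-month visit = first possible procedure + 3 months = 1 December 2021 + 3 months = 1 March 2022.
- Last possible procedure = 31 January 2022.
- Gap = 28 days (to 28 February) + 1 = 29 days.
- Last 3-month visit = 31 January 2022 + 3 months = about 30 April 2022.

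The treatment stage is 31 + 31 = 62 days and the wait to the visit is 31 + 31 + 28 = 90 days for the first patient. No patient stented within the stage can reach the visit before the stage ends.

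**3. What is the origin for controls?** The time point counts from surgery. Controls receive aspirin only, and Section V describes their treatment as starting a drug ("Arrange stent placement surgery or start standard drug treatment for eligible patients"). No date is given from which their 3 months run.

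**4. A generous reading (hypothetical).** Suppose the regular follow-up meant a contact with everyone on 1 February 2022, the first day of that stage. The wait after treatment would run from 1 day (treated 31 January) to 62 days (treated 1 December), with mean (1 + 62)/2 = 31.5 days if treatment is spread evenly. It would exceed 7 days for 55 of 62 stage days (89%) and 30 days for 32 of 62 (52%). Even this contact comes after all stenting is over. No such visit is written.

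**5. What a running review could show (assumed rates and interval).** The chance of at least one event in the first 5 procedures is 1 − (1 − p)^5:

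| Assumed event rate p | At least 1 event in first 5 | Expected events, arm of 20 (20 × p) |
|---|---|---|
| 5% | 1 − 0.95^5 = 23% | 1 |
| 10% | 1 − 0.90^5 = 41% | 2 |
| 20% | 1 − 0.80^5 = 67% | 4 |

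The rates, the arm size of 20 and the interval of 5 are mine. The conclusion does not depend on them.

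**6. Does randomisation work as the common origin?** It exists for every patient, including one assigned to a stent who never receives it, and it catches events between assignment and surgery. But Section III.3 places it after consent, Section V places consent in May to November 2021, and randomisation itself is not dated. A patient randomised on 1 May 2021 would reach 3 months on 1 August 2021, four months before the first possible procedure on 1 December 2021. The origin is sound only if patients are randomised shortly before treatment.

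**The case against.** The strongest reply is that this is a very short document and silence is not refusal. The outcome list is introduced by *including*, so it is open. Follow-up is called regular, and its stage runs to February 2023, ten months past the last 3-month visit (May 2022 to February 2023), which suggests that more contacts may be intended. The plan cites ethics approval and adherence to ethical standards, and it foresees a data management system. The Section V entries may be project milestones and not strict windows for each patient.

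Much of this stands, and it rules out several stronger readings that a reader might infer:

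- *That the study will have no safety data.* The open list does not support this. What can be said is that no safety outcome is named or defined, so consistent collection and comparison are not assured.
- *That complications would go unseen.* Clinical staff would see an acute event. The gap is that the plan does not say it is recorded, counted, reviewed or compared.
- *That a patient who dies early has no value for any outcome.* The plan names no neurological scale, so death might receive a score. Blood flow could be read from angiography at the procedure, and reocclusion could be seen before death. The supportable statement is that the handling of death is unspecified.
- *That the waits in step 4 or the rates in step 5 describe this trial.* They rest on an unwritten visit and on assumed rates.

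What does not stand is that the general statements fill the gap. An ethics approval and a database do not define an event, set a time for asking about it, or give controls an origin.

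**Conclusion.** The point holds. Safety is a co-equal aim without a named outcome, and the one time point is undefined for one of the two groups. On the stated calendar the earliest scheduled assessment comes 29 days after the last possible stent. Followed as written, the schedule captures no early procedural harm, cannot inform whether stenting continues, and does not specify a between-group safety comparison.

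The 29 days assume that the stage dates are the actual treatment window and that no unnamed visit is held. How far results would be distorted cannot be computed from the documents.

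A reader might also infer that a numerical stopping limit is needed. The documents give no acceptable event rate from which to set one, and a limit in a small arm errs in both directions. For example, pausing at 2 events in the first 5 procedures or 3 in the first 10 would pause an arm of 10 with probability about 3% at a true rate of 5%, 11% at 10% and only 39% at 20%. At 20% it would therefore miss 61% of the time. A documented review is enough here.

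**What to change.** In Section V, replace the time-point sentence with:

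> Patients are randomised shortly before treatment is due to start. Any stroke, intracranial haemorrhage and death are recorded in both groups from randomisation to 3 months, and compared by assigned group with Fisher's exact test. In the stent group, events and procedural complications (including vessel perforation and access-site bleeding) are also recorded during the procedure, in hospital and at about day 7. All patients have a brief early contact (about day 7 after surgery or after the start of study drug treatment) and a 3-month assessment timed from randomisation in both groups. Serious events are reported promptly to the ethics committee. The investigator documents a review of the cumulative count at regular intervals during the treatment stage (for example after every 5 procedures) and whether stenting continues.

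The opening sentence is needed because of step 6 of the working. Day 7 and the interval of 5 are practical choices that the sponsor may vary. Each event also needs a one-line definition.

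The cost is one short contact per patient (by telephone if discharged), a running event list in the data management system already planned, and brief reviews: n/5 of them, so 2, 4, 6 or 8 for an assumed stent arm of 10, 20, 30 or 40. Fisher's exact test is already in Section IV. The reviews involve no interim test and no automatic stop.
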